6.0 STRATIFICATION/DESCRIPTIVE FACTORS/RANDOMIZATION SCHEME

The site of enteral feeding tube placement will be randomized. Subjects will be not be stratified.

7.0 STUDY AGENT ADMINISTRATION OR INTERVENTION AND TOXICITY MANAGEMENT PLAN NA

8.0 ASSESSMENT OF EFFICACY AND SAFETY

Safety of this study plan has been reviewed with the multidisciplinary team and by review of relevant literature. Steps taken to minimize potential risks are summarized in table 4.

The following study team members, who are all USC faculty members have evaluated aspects of this protocol related to their area of expertise and have concluded that this is a low risk study, with potential benefit outweighing possible harm.

Specifically:

- a. Stability and safety of oral anchor: Orthodontists: [name] DDS and [name] DDS (resident)
- b. Stability of orojejunal tube in anchor: Bioengineer [name] PhD
- c. Safety of orojejunal tube in oropharynx: ENT: [name] MD
- d. Safety of orojejunal tube in gastrointestinal tract and low calorie diet similar to that post gastric bypass surgery: Foregut and Bariatric Surgeon and Endoscopist: [name] MD
- e. Safety of nutritional intervention and diabetes management: Endocrinologists [name] MD, [name] DO

Oropharyngeal Care with Anchor and Tube In-Situ

Standard care as used following placement of orthodontic braces will be recommended. Subjects will be advised to brush and floss their teeth after every meal. Complications are not anticipated even in subjects with type 2 diabetes. Acetaminophen liquid may be taken in standard doses if needed to decrease tube discomfort.

The anchors will be manufactured in-house by [name] using medical-grade orthodontic materials. The anchor will be bonded to the molar using fluoride containing cement to minimize the unlikely possibility of dental decay. The anchors will be placed and removed by the study team orthodontists.

It is considered highly unlikely that infection will develop due to use of the tube anywhere along its path. If fever develops for any reason however, whether considered due to the intervention per se or to intercurrent illness, the subject will be removed from the study.

Very Low Calorie and Low Calorie Tube Feeds

Cappello et al [26] reported on the use of a very low calorie nasogastric tube feed diet (200-260 kcal/d) for 10 day periods with no

serious complications in a group of over 19,000 people. The problems encountered were damage to the external part of the tube (e.g. shaving) 2%, “gastric hypersecretion” (nos) 2%, nausea and vomiting 1%, and intolerance to the nasal tube 0.03%. The following were not observed: ulceration or bleeding due to the tube, breakage of the tube in esophagus or in the stomach, perforation or bleeding of the stomach. Sukkar et al [42] in another similar smaller study reported on 22 patients who received 10 days of very low calorie nasogastric tube feeds (200-260 kcal/d). Subjects were monitored for the following side effects relating to enteral nutrition (abdominal distension and pain, diarrhea, vomiting, reflux, naso-gastric, tube obstruction, de-positioning or accidental removal of the naso-gastric tube, others) and those related to the very low calorie/high protein diet (cardiac arrhythmia, ketosis, hypoglycemia, others). Out of 26 patients enrolled, 3 patients (9 %) were withdrawn due to poor compliance and 1 (3 %) for allergy to milk protein. Of the remaining 22 subjects there were no reported major complications or side effects resulting from the enteral nutrition in any patient. In particular, no cardiac arrhythmias were reported, nor diarrhea or cramps. The following were reported: constipation (3/22; 13.6 %), dizziness or headache during the first 2 days [20/22; 90.9 % (only two needed medication)], general weakness (3/22; 13.6 %), halitosis (5/22; 22.7 %) controlled by sugarless mint chewing-gum. The naso-gastric tube was blocked in 3 patients and required repositioning.

Enteral Feeding Tube Placement

Although enteral tube placement is a common clinical practice and is performed by lay individuals in the home environment when necessary, it has been associated with serious complications including malposition into the airway, perforation of the trachea and esophagus and pneumothorax. These complications occur almost exclusively during blind intubation in sedated, unconscious or otherwise poorly responsive patients and neonates and when the tube is placed through the nasopharynx. In this study we will use the EAS™ system and CORTAK tubes which have demonstrated greater safety than standard blind placement due to real time visualization during placements. Tubes will be placed following manufacturer’s recommended procedure to minimize risk. Furthermore all subjects will be fully alert throughout the procedure and able to interact with the trained investigator who is placing the tube; tubes will be placed by the oral route with a “swallow down” placement technique rather than a “push” technique. These precautions can be expected to minimize the already very low rate of complications that can arise during tube placement, making a serious problem extremely unlikely. Aspiration of stomach contents may occur if the subject has not fasted prior to tube placement. If on enquiry the subject has not fasted then the test will be cancelled. Blind intubation requires x-ray confirmation prior to tube use to minimize complications related to tube misplacement however the EAS™ system is FDA approved to not require x-ray confirmation of placement thereby avoiding risks associated with radiation. [35-41]

Ambulatory Use of Jejun Tube for 14 Days Nasal and oral feeding tube for feeds are standard accepted clinical practice for subjects requiring nutritional support up to 30 days. The American Gastroenterological Society recommends that consideration be given to replacing a naso or oro enteral feeding tube with a percutaneous tube after 30days. [43] Although not currently widely accepted as medical therapy, the ketogenic enteric diet has been extensively used in Europe and is now available through franchises internationally. Although the underlying physiological approach that we are hypothesizing is markedly different to this diet, it does demonstrate that use of enteral tubes for 10 days is feasible and acceptable to many individuals having been used in over 24,000 subjects in one center. [26] This study involves a variant of standard enteral tube feeding, the main differences being the indication for the intervention and the rate of the tube feed administration. Subjects in this study will be far more closely monitored than in standard clinical practice. Some discomfort can be expected to occur in the throat due to the tube and may be relieved by slight relocation of the tube to relieve pressure or overall body repositioning of the e.g. lying down after prolonged sitting at a desk. Discomfort tends to decrease after 4-5 days of use. Acetaminophen will be offered to subjects for use if desired. If fever develops suggestive of local infection then the subject will be withdrawn from the study and referred to their usual care provider for further management. This problems has not however been reported in thousands of patients undergoing the ketogenc enteric diet.[26, 42]

Inadvertent Dislodgement of the Tube

The tube anchor is located on the upper posterior buccal molar. The 140cm tube immediately passes backwards from the anchor to the lateral oropharynx where it descends straight down into the gastrointestinal tract. It is maintained in this position by gravity and peristalsis. The tube is thus unable to move medially across the occlusal surface of the teeth and hence bruxism does not pose a risk.

Mouth guards

Participants are not required to wear a mouth guard either while awake or asleep as the tube is positioned well lateral and posterior occlusal surfaces of the teeth.

Precautions to be taken to prevent the tube being accidentally swallowed

The following precautions will be taken to decrease the chance that the tube will be accidentally swallowed: Participants will be asked to monitor for any loosening of the molar band daily and also to monitor for any evidence of abrasion or wear on the intraoral portion of the tube. They will do this by checking that the band is secure manually and by looking for wear on the tube when it is brought slightly forward to be attached to the syringe for each tube feeding. They will be requested to report any concerns in this regard to the study team as soon as it is detected. They will also be told how to remove the band or tube if it should become so loose or worn that it could dislodge spontaneously. Furthermore to decrease risk of the band becoming dislodged the band will be kept in place for as short a period as possible.

Procedure if the tube is accidentally swallowed and how it will be retrieved.

The risk of accidental swallowing of the tube is considered to be extremely remote due to the precautions taken in the design of the anchor and tube as described above. If the tube is accidentally swallowed the participant will contact the study team and co-investigator [name] who is a foregut surgeon and endoscopist. He will arrange appropriate follow-up for the participant. Clinical back-up in this area will be provided by co-investigator [name] (gastroenterologist and endoscopist). References for the following data can be found in the recent systematic review of the topic of ingested foreign bodies in adults. [47] As most ingested foreign bodies pass through the gastrointestinal tract without any difficulty conservative treatment by means of close observation will likely be the approach used. This is the treatment of choice as the tube is blunt and narrow (<2.5 cm diameter) and the tip will already be past the pylorus. Spontaneous passage can be expected within 4–6 days. Rare cases have been reported where it has taken up to 4 weeks to pass a foreign object. Until the tube has passed, the participant will be asked to monitor their stools continuously. No change in eating behavior will be required during this period. If the tube is not passed after about 1 week then weekly outpatient x-ray examination will likely be recommended in order to document, the foreign body's passage. As the tube is radiopaque its passage can be documented. (See product insert uploaded at iSTAR #18.2).

If the tube does not pass spontaneously then it may be retrieved by [name] or [name] using upper or lower endoscopy. It is unlikely that emergency esophagogastroduodenoscopy (EGD) will be required as this is recommended when the esophagus is completely occluded (because of the risk of aspiration and/or pressure necrosis), when the ingested object has a sharp point or edge (because of the risk of perforation, with ensuing mediastinitis or peritonitis), and when a battery has been ingested (because of the risk of necrosis and fistula formation)-none of which can reasonably be expected to occur in this study. Similarly even an urgent but non-emergency EGD (within 12 to 24) hours is unlikely to be required as this is recommended for non-occluding esophageal foreign bodies such as magnets. Recovery of a foreign body by means of colonoscopy is not common practice according to the available data as after the ileocecal valve has been passed the foreign body is usually excreted without any complications.

There is a remote possibility that surgery (including the option of minimally invasive laparoscopic surgery) could be required to remove the tube. This has become progressively more unusual as endoscopic retrieval rates improve. The only absolute indication for surgery is reported to be perforation which is highly unlikely to occur with the blunt soft tube. Relative indications for surgery after ingestion of foreign bodies exist in the case of complications that cannot be resolved endoscopically or after unsuccessful attempts at endoscopic recovery.

Data to support claims that the tube will almost certainly pass spontaneously through the intestinal tract without any intestinal abnormalities

A recent review by Ambe et al [47] summarizes findings from numerous articles on the topic of ingested foreign bodies in adult. It has been widely reported that the majority of foreign bodies in the gastrointestinal tract will pass spontaneously but that about 10-20% will require non-operative intervention and less than 1% will require surgery. In the current study, in the very unlikely event that the tube were to be accidentally ingested, the rate of spontaneous passage can be expected to be far higher than 80%. The reasons for this are as follows:

- a. Impaction most often occurs at areas of acute angulation or physiologic narrowing. The esophagus is the most frequent site of blockage (50–75%) because of physiological narrowing at the cricopharyngeal sphincter, the aortic arch and the diaphragmatic hiatus. Other relatively narrow and angled areas are the duodenum and the entrance to the jejunum at the Ligament of Treitz. In this study the tube will be placed by the study team through the esophagus, the duodenum

and beyond the ligament of Treitz so obstruction at these levels would be extremely unlikely. Once through the esophagus, the majority of ingested foreign bodies pass through the alimentary tract uneventfully.

- b. Patients with prior gastrointestinal tract surgery or congenital gut malformations account for a large number of obstructions. We will reduce the risk of obstruction by the exclusion criteria of a history of abdominal infections or surgeries or other illnesses that could lead to strictures or adhesions.
- c. The participant will be excluded from the trial if the tube cannot be passed through the esophagus, stomach, duodenum and jejunum initially, the commonest sites for impaction.

Daily Activities with Tube In-Situ

The intra-oral tube placement renders it inapparent to the casual observer. This allows the subject to avoid embarrassment or unwanted explanations due to tube use and to continue with routine activities. The subject may experience discomfort or some anxiety due to tube placement and if rapid weight loss occurs, may experience increased fatigue. As this is a voluntary study the subject will have made an informed decision to have a tube in-situ for 2 weeks. Where possible, the tube will be placed during a 2 week period when the subject will be able to adhere to the study routine and rest appropriately. Ease of mind will likely be increased for the subject by knowing that at any time they desire they can remove the tube themselves, withdraw from the study and/or contact the study team.

Symptoms due to Jejunal Nutrient Administration

Subjects may experience dumping symptoms of nausea, palpitations, sweating and abdominal pain during or for about 1 hour after jejunal nutrient infusion. The dose of the nutrient administered will be selected by the subject to achieve comfortable satiety. They will stop administering nutrient if they experience unpleasant symptoms. Symptoms, if they occur are usually mild and are transient and self-limited. We will exclude potential subjects from the study if they have any known cardiovascular disease (other than controlled hypertension) to minimize potential risks to the subject associated with possible palpitations in association with dumping syndrome.

Venipuncture

This study involves venipuncture of a peripheral vein. This is associated with a small risk of minor bleeding and infection at the puncture site. To minimize this risk, aseptic precautions will be used.

Risk of Hypoglycemia or Hyperglycemia

Alteration in diet and physical activity could lead to alterations in blood glucose: both hyperglycemia and hypoglycemia.

To minimize the risk of these complications the following precautions will be made:

- a. All participants will have the symptoms and signs of hyperglycemia and hypoglycemia reviewed with them as well as recommended management at each visit starting with the recruitment visit when the protocol is reviewed.
- b. As most diabetic patients eating very low-calorie diets have marked improvement in hyperglycemia with blood glucose concentrations falling within the first one to two weeks oral hypoglycemic drugs will be discontinued for the first week of therapy. [33] An increase in activity level may also cause a fall in blood glucose levels. To aid in maintaining safe blood glucose levels subjects will be required to report to the study team if their blood glucose is over 250mg/dl on more than 2 consecutive measures or any value is over 300mg/dl or less than 70mg/dl on any occasion.
- c. Information on managing hypoglycemia is provided in the FREE TO GO Study Instructions given to the participant.

Table 4 Summary of Steps Taken to Minimize Risk of Intervention

Concern	Precaution
Modified anchoring of orojejunal tube	Development by senior bioengineering and orthodontic specialists
Safety of orojejunal tube for 2 weeks	Potential risks reviewed with senior ENT and bariatric surgeon and deemed highly unlikely to occur Subjects will monitor their temperature and the tube position daily and report to the study team if any concerns

Physical and psychosocial discomfort due to ambulatory use of orojejunal tube for 2 weeks	Intraoral anchoring makes tube inapparent to observers. They will be encouraged to take acetaminophen and take other steps to decrease discomfort of tube particularly in first few days of use. They will be shown how to remove the tube themselves at any time if they so desire
Back-up in event of distal tube displacement	Senior bariatric surgeon on study team
Safety of very low calorie diet for 2 weeks in subjects with type 2 diabetes	Close monitoring by specialist endocrinologist with adjustment of medication if needed. All subjects can take food and liquid ad lib. Mandatory minimum 480 kcal/d; 1.6litres fluid/day; 100% RDA high quality protein; 100% RDA electrolytes, minerals and vitamins.
Hyper- and Hypo-glycemia	Oral hypoglycemic drugs will be discontinued for the first week of therapy and participants will contact the study team if their glucose levels are less than 70mg/dL or over 250mg/dL. Participants will be educated on the symptoms of hypo- and hyper- glycemia and provided wth instruction and glucose tablets for the management of hypoglycemia.

9.0 CLINICAL AND LABORATORY EVALUATIONS AND STUDY CALENDAR

Table 5

	Preparation			With Tube		Follow Up	
	Approximately Day-14	Approximately Day -7	Day 0	Day 7	Day 14	Day 21am	Day 28
Location ALL at EDWARD R. ROYBAL CHC							
Clinical Evaluation	By orthodontist for suitability for molar band	By orthodontist for placement of molar band (may require 2 visits)	By MD Vital Signs Symptoms Physical Exam Weight Waist Hip	By MD Vital Signs Symptoms Physical Exam Weight Waist Hip	By MD Vital Signs Symptoms Physical Exam Weight Waist Hip	By MD Vital Signs Symptoms Physical Exam Weight Waist Hip	By MD Vital Signs Symptoms Physical Exam Weight Waist Hip
Labs (total 20 cc/visit)	none	none	BMP ^a Fasting: Adiponectin ^b Leptin ^b FGF-19 ^b Insulin ^b Glucose ^b C-peptide ^b GLP-1 ^c Ghrelin ^c PYY ^c CCK ^c Bile Acids ^c FT3 ^c		BMP ^a Fasting: Adiponectin ^b Leptin ^b FGF-19 ^b Insulin ^b Glucose ^b C-peptide ^b GLP-1 ^c Ghrelin ^c PYY ^c CCK ^c Bile Acids ^c FT3 ^c		BMP ^a Fasting: Adiponectin ^b Leptin ^b FGF-19 ^b Insulin ^b Glucose ^b C-peptide ^b GLP-1 ^c Ghrelin ^c PYY ^c CCK ^c Bile Acids ^c FT3 ^c
Procedure	Place spacers	Place band	Place tube Place FitBit Body Composition Provide 1 week food	Return all uneaten food Provide 1 week food	Return all uneaten food Remove tube and band Body Composition		Remove FitBit Body Composition
Other Activities	none	Start Daily Flow Sheet	Review daily flowsheet including self-monitored blood glucose	Review daily flow sheet including self-monitored blood glucose Download FitBit/recharge	Review daily flow sheet including self-monitored blood glucose Download FitBit/recharge	Review daily flow sheet including self-monitored blood glucose Download FitBit/recharge	Review daily flow sheet including self-monitored blood glucose Remove and download FitBit
Food Intake	Ad lib		Day 0-Day 14 Tube Bolus and Provided Diet Ad lib free foods Supplements		Day 14-Day 28 Ad lib		

^aat USC DORI ^bat Cedars-Sinai ^cat Cedars Sinai when funds available

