Day 0: Subject presents fasting to the CHC. Blood pressure, heart rate, weight, height and waist circumference and body composition on InBody520 BioSpace will be recorded. FitBit® activity monitor placed. Subjects will have a jejunal feeding tube placed by the investigator using a CORPAK EAS™ and will then be randomized to the control or intervention group.

Day 0-Day 14: Subjects will take a mixed meal or electrolyte solution at a prescribed rate and interval and will be requested to eat ad lib only from provided meals of known caloric amount or from a list of low calorie items. Subjects will maintain a log of all food intake, temperature at least daily, tube position and symptoms and blood glucose 4 times a day.

Day 7: The subject will return to the CHC for review for continuation in the study, of their log and caloric intake and for adjustment of medication if necessary and activity monitor download.

Day 14: Day 0 measures will be repeated at the CHC and the tube removed. All uneaten food will be returned for caloric intake determination, activity monitor download.

Day 15-Day 28: The subject will maintain a medication and blood glucose log for 14 days after the removal of the tube.

Day 28: Exit outcome measures similar to those at Day 0.

Safety: The subjects will be monitored for fever, sore throat, displacement of the tube, gastrointestinal upset, vital signs, biochemical measures and weight change, and if pre-specified criteria are met or in the clinical judgment of the PI it is not appropriate to continue, will be withdrawn from the study.

Outcome Measures: weight change, caloric intake, waist and hip measurement, hormones and biochemical measures, physical activity, body composition, select symptoms, medication use, average self-monitored blood glucose level

Reimbursement: Subjects will receive standardized meals of known caloric amount for 2 weeks and up to \$300 cash.

Statistics This is a pilot study and sample size estimates are not appropriate. However based on studies of dietary restriction with a 1250 kcal diet for 1 week we anticipate identifying a significantly greater weight loss in the intervention arm with a sample size of 10 subjects/group. Fifteen subjects/group will be enrolled to allow for drop-outs.

Analysis: Primary analysis will be to compare change from baseline in outcome measures between the 2 groups using paired t-test. SC CTSI Biostatistics Department has aided in the study design.

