There may be as little as 2 days or as long as several weeks from the time the spacers are placed to the time the tube is placed depending on subject and study team member availability and technical aspects of the band and tube placement (i.e. how long it takes for the spacers to separate the teeth adequately, whether the subject requires 1 or 2 visits to fit the molar band and whether the subject has the tube placed the same day as the molar band).

Day 0: The subject will be seen at the CHC in the fasted state. All women between 18 and 50 years of age who have not undergone hysterectomy or tubal ligation will undergo a urine pregnancy test. If the test is positive then they will not be eligible to participate. Baseline vital signs, weight, height and waist and hip circumference will be recorded and baseline labs drawn. Body composition will be measured by the Biospace InBody 520 device (Biospace, Cerritos CA 90703 <http://www.biospaceamerica.com/>). This device measures body composition non-invasively as the subject stands on a scale-like device while grasping two handles – one in each hand. The device works by sending a very low voltage electrical signal through the body to determine water content, body fat percentage, and lean mass. The machine will be kept in the basement of the CHC. The FitBit Monitor is placed on the subject's wrist or clothing and will record activity for up to 2 weeks at a time without need for any adjustment by the wearer.

Body weight will be measured in the morning on a calibrated scale with the subject wearing light clothing. Waist circumference will be measured by wrapping a flexible measuring tape around the narrowest point of the midsection. The tape will be kept parallel to the floor. Hip circumference will be measured by wrapping a flexible tape around the hips at the widest diameter of the buttocks. The tape will be kept parallel to the floor. The waist-to-hip ratio will be determined by taking the waist circumference and dividing by the hip circumference.

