10.0 CRITERIA FOR EVALUATION AND ENDPOINT DEFINITIONS

Primary aim: weight change immediately following the intervention period between the study groups

Secondary aims: to compare the following within and between groups:

- a. From Day 0 to Day 14: caloric intake (as determined by consumption of provided food)
- b. From Day 0 to Day 14: weight change (within group)
- c. From Day 0 to Day 28: weight change
- d. From Day 0 to Day 14 and also from Day 0 to Day 28: waist and hip measurement, hormones and biochemical measures, physical activity, body composition, select symptoms, medication use, average self-monitored blood glucose level

11.0 SPECIAL INSTRUCTIONS:

Samples will be collected by the PI or IRB approved research assistant from peripheral venipuncture.

The investigator will draw 20cc fasting blood at Day 0, 14 and 28 visits into a prepared tube containing aprotinin. This will be kept on ice and centrifuged, separated and aliquoted within 30mins of blood draw. Samples will then be stored at -20 degrees centigrade until transferred on ice to collaborator for assay.

Study Costs: All costs for this study will be paid from study funds. There will be no patient care costs incurred for payment from non-study funds. Costs covered by the study include study visits, supplies, equipment, blood draws, biochemical analysis and subject reimbursement.

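### Physical activity has no pre-intervention baseline, because the monitor is first worn at the visit where the tube is placed and treatment starts

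*Combined protocol and SAP*

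**What the plan says.** Section 10.0 (and Section 2.0) lists the secondary outcomes to be compared within and between groups: "From Day 0 to Day 14 and also from Day 0 to Day 28: waist and hip measurement, hormones and biochemical measures, physical activity". The synopsis states the analysis in general terms: "Primary analysis will be to compare change from baseline in outcome measures between the 2 groups". Physical activity is among the outcome measures listed there.

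The monitor appears first on Day 0. In Table 5 (Section 9.0) the Day 0 procedures read "Place tube Place FitBit Body Composition Provide 1 week food". The synopsis has "FitBit® activity monitor placed. Subjects will have a jejunal feeding tube placed by the investigator", and the Day 0 text of Section 3.0 says "The FitBit Monitor is placed on the subject's wrist or clothing and will record activity for up to 2 weeks at a time". Section 3.0 places randomisation at the same visit and has the subject take the first tube bolus before going home.

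The first "Download FitBit/recharge" entry in Table 5 is at Day 7; none is listed at Day 0. The one record that begins earlier is the log, "Start Daily Flow Sheet", at about Day -7. The form for the periods before and after the tube (Appendix C) has fields for time, blood glucose and medication only.

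Section 13.0 counts the same comparisons from Day 1, lists them as between-group, and plans repeated-measures ANOVA for change over time.

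**The concern.** Weight, waist, body composition and blood samples can be taken in minutes on the morning of Day 0, before anything is done to the subject. Activity is different: it accumulates over days, so a device put on at the Day 0 visit cannot give a usual level for that subject before the intervention.

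The early days with the tube are a poor stand-in. Section 4.4 expects throat discomfort mostly in the first 4-5 days. Section 8.0 hopes that, where possible, the tube period will be one in which the subject can rest, and mentions fatigue if weight falls quickly. Section 3.0 leaves subjects free to change their activity. Follow-up days do not serve either, since the hypothesis is that effects last for two weeks after the tube is removed.

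Two things are at stake. The pilot is meant to supply effect sizes and parameter estimates for later studies (Section 13.0), and on this schedule it cannot supply the change in activity from a pre-intervention level, or the spread of that change. The between-group comparison also loses a covariate that could be useful with 10 to 15 subjects per group.

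**Working it through.** The documents give no figure on this point, so there is none to reproduce. The main check is of the schedule; the arithmetic after it is an illustration.

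**Schedule**

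| Item | When | Source |
|---|---|---|
| Daily log starts, no activity field | about Day -7 | Table 5, Appendix C |
| Monitor first worn | Day 0 visit | Synopsis, Section 3.0, Table 5 |
| Tube placed, subject randomised, first bolus | Day 0 visit | Synopsis, Section 3.0 |
| First monitor download | Day 7 | Table 5 |
| Later downloads | Days 14, 21, 28 | Table 5 |

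Full days of activity recorded before the Day 0 visit: 0. Days with the tube: 14. Follow-up days: 14. Wear before treatment is at most part of one clinic visit. The exception is a subject whose tube is not in position at first: feeds then wait a day or 2, but the tube is already in.

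**What a baseline would be worth**

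Assumptions, none from the documents: equal variance at baseline and on study, and a correlation ρ of 0.5 to 0.8 between the two. The standard error of the between-group difference, relative to using on-study activity alone, is

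- covariance adjustment (ANCOVA): √(1 − ρ²)
- simple change score: √(2(1 − ρ))

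| ρ | ANCOVA ratio | Reduction | Change-score ratio | Reduction |
|---|---|---|---|---|
| 0.5 | √0.75 = 0.87 | 13% | √1.00 = 1.00 | 0% |
| 0.8 | √0.36 = 0.60 | 40% | √0.40 = 0.63 | 37% |

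The share of between-person variance that the covariate removes is ρ², so 25% to 64%. The equivalent gain in sample size with ANCOVA is 1/(1 − ρ²), so 1.33 to 2.78 times.

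Detectable difference (two-sided 5%, 80% power) = (1.96 + 0.84) × SD × √(2/n), times the ANCOVA ratio where a baseline exists:

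| n per group | No baseline | ANCOVA, ρ = 0.5 | ANCOVA, ρ = 0.7 | ANCOVA, ρ = 0.8 |
|---|---|---|---|---|
| 10 | 1.25 SD | 1.09 SD | 0.89 SD | 0.75 SD |
| 15 | 1.02 SD | 0.89 SD | 0.73 SD | 0.61 SD |

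These use the normal approximation and ignore the one degree of freedom spent on the covariate.

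**The case against.** The best case for the plan is that activity need not be read as a change score. Sections 2.0 and 10.0 speak of weight change for weight, but for activity they only name the periods, much as they do for caloric intake, which is a total over Day 0 to Day 14. Read that way, mean activity per period can be compared between groups with no baseline, and randomisation makes that comparison valid. Both groups have the tube, so early discomfort is expected in both and does not by itself bias the contrast. Downloads on Days 7, 14, 21 and 28 also allow tube days to be compared with follow-up days within a group. All of this stands. It does not supply a pre-intervention reference, and the synopsis does call for change from baseline in the outcome measures.

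A reader might go further than the documents allow in four ways.

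- That the monitor goes on after the tube. This rests on the order of items in one cell of Table 5; the synopsis and Section 3.0 mention the monitor first. All of it is one visit, so the order matters little.
- That there is no baseline value at all. Section 13.0 would take Day 1, which yields a number, though one normally recorded on treatment.
- That every within-group question on activity is lost. Only change from usual activity is.
- That a baseline would remove most of the between-person variation. That needs ρ above about 0.71.

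The larger precision gain also depends on ANCOVA, which is not planned. With a change score the gain at ρ = 0.5 is nil.

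Finally, activity is one of many secondary outcomes in a pilot that disclaims power. That limits the weight of the point. It does not remove it, since the correction is cheap.

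**Conclusion.** The point holds in a limited form. No full day of activity is recorded before the visit at which the tube is placed and the first bolus taken, so change from usual activity cannot be estimated within group. The between-group comparison of activity per period is valid, with a loss of precision only. The primary weight endpoint has its own Day 0 measurement and is not touched.

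The schedule finding rests on the documents alone. The size of the precision loss rests on an assumed correlation, and would be smaller if a baseline of only a few days correlated weakly with later activity. Some subject-instruction pages were not in the text available for this review, so any instruction there on wearing the monitor could not be checked.

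**What to change.** 1. Issue the same monitor at the band visit (about Day -7), when the daily flow sheet already starts. If band and tube are expected on the same day, issue it at the spacer visit.
2. Add a download and recharge on Day 0, before the tube is placed.
3. Define baseline as mean daily activity over a fixed window before the tube, for example up to the last 7 days, with a stated minimum number of valid days.
4. Analyse on-tube and follow-up activity by ANCOVA on that baseline, and name the same starting day in Sections 10.0 and 13.0.

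If this is not done, redefine the endpoint as mean activity per period compared between groups, and drop the change-from-Day-0 wording for activity.

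The cost is one extra download and recharge, with no new device or visit. There are two drawbacks. Section 3.0 lets the preparation gap run from 2 days to several weeks, so baseline length will vary. The monitor "will record activity for up to 2 weeks at a time", so in a long gap it could stop before Day 0 and lose the days nearest the tube unless it is recharged or issued later. Whether band and tube will share a day may also not be known at the spacer visit, so some subjects may have a short baseline or none; the plan should say how they are handled.
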